5.3.3 Efficacy Variables

Term	Definition
Endoscopic Improvement	SES-CD \leq 4 with an Ulcerated Surface subscore no greater than 1 in any segment
CDAI Remission	CDAI $<$ 150
SFPS Remission	SFPS $<$ 50
Response per CDAI	A reduction in CDAI by \geq 70 (CR-70) from baseline*
Enhanced response per CDAI	Decrease in CDAI \geq 100 (CR-100) from baseline*
Endoscopic response	Decrease \geq 50% SES-CD from Baseline
IBDQ Response	Increase in IBDQ score \geq 16 point from Baseline*
IBDQ Remission	IBDQ \geq 170

* Baseline in the additional efficacy variables is defined as the Baseline in Study M14-115.

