3.0 Introduction

This statistical analysis plan (SAP) describes the statistical analysis to be completed by the AbbVie Clinical Statistics Department for Study M14-347.

It provides details to further elaborate statistical methods as outlined in the protocol and describes analysis conventions to guide the statistical programming work.

This analysis plan describes the primary and secondary efficacy analyses as well as the safety analysis of data except pharmacokinetic, serological and mRNA biomarkers which will be analyzed separately. It takes into account ICH Guidelines E3 and E9.

Unless noted otherwise, all analyses will be performed using SAS version 9.2 or later (SAS Institute Inc., Cary, NC 27513) under the UNIX operating system.

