If a subject met the censoring criteria for CD related concomitant therapy during Study M14-115, all binary efficacy endpoints will be No in Study M14-347, all observed values in Study M14-347 will be replaced by Study M14-115 Baseline values.

Dose Escalation

Subjects who had dose escalated to 40 mg ew will be censored for efficacy assessments (i.e., will be considered non-responders for categorical endpoints and will have

Study M14-115 Baseline values carried forward for non-categorical assessments) from that point through the end of the study.

Definition of Missing Data Imputation

Missing data imputation will be done only for efficacy variables (categorical and continuous variables). For the analysis other than efficacy, no imputation will be done for missing values.

Non-Responder Imputation (NRI)

The NRI approach is used for binary efficacy data. These variables can take values of 'Achieved' or 'Not Achieved' or may be missing for any reason including discontinuation from study. According to the NRI imputation approach, all missing values will be considered as 'Not Achieved.'

Observed Case (OC)

Observed case analysis will be performed such that missing values will not be imputed. However, all observed values will be replaced by Study M14-115 Baseline value once subjects met the censoring criteria for CD-related concomitant therapy or dose escalation, whichever is earlier.

Last Observation Carried Forward (LOCF)

For all variables (categorical variables and continuous variables), the following rules will be used for the LOCF approach:

1. Baseline and Pre-Baseline values will not be used to impute the missing Post-Baseline values.
2. Missing values after Study Day 1 will be imputed using the latest non-missing values after Day 1 and prior to the missing value. If there are no non-missing values after Baseline, then the LOCF value will be missing.

Rule for CDAI Calculation

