For Study M14-347, both Roche and Abbott platform are used to measure hs-CRP. The study team has decided to use Abbott platform for CSR analysis. If hs-CRP was measured by Roche platform only, the value will be converted to Abbott equivalent by a conversion factor.

Definition of Endoscopic Improvement

SES-CD \leq 4 and at least two point reduction from Study M14-115 Baseline and no subscore > 1 in any individual variable.

Definition of CDAI Remission

CDAI $<$ 150

Definition of SFPS Remission

SFPS $<$ 50

Definition of CDAI Response

Decrease in CDAI \geq 70 points from Study M14-115 Baseline

Definition of Enhanced CDAI Response

Decrease in CDAI \geq 100 points from Study M14-115 Baseline

Definition of Endoscopic Response

Decrease in SES-CD $>$ 50% from Study M14-115 Baseline

Definition of IBDQ Response

Increase in IBDQ \geq 16 from Study M14-115 Baseline

Definition of IBDQ Remission

IBDQ \geq 170

Definition of Symptomatic Remission

Average daily stool frequency \leq 1.5 and not worse than Study M14-115 Induction baseline AND average daily abdominal pain \leq 1.0 and not worse than Study M14-115 Induction baseline.

Definition of Symptomatic Response

Average daily stool frequency at least 30% reduction from Study M14-115 Induction baseline and average daily abdominal pain not worse than Study M14-115 Induction baseline OR average daily abdominal pain at least 30% reduction from Study M14-115 Induction baseline and average daily stool frequency not worse than Study M14-115 Induction baseline.

Discontinued Corticosteroid Use at Each Visit Among Subjects Who Used Corticosteroids at Week 0 of Study M14-347

Discontinued steroid use at each visit is based on the steroid use on the date of CDAI measurement for that visit. If the subject has no CDAI for the visit, the steroid use on the nominal day for that visit ([Table 3](#)) will be evaluated.

If a subject discontinued the study, 'discontinued corticosteroid use' will be classified as No from that point through the end of the study.

If a subject met censoring criteria for CD-related concomitant therapy or dose escalation, whichever is earlier, 'discontinued steroid use' will be classified as No from that point through the end of the study.

EuroQol-5D-5L (EQ-5D)

EQ-5D is a standardized measure of health status developed by the EuroQol Group in order to provide a simple, generic measure of health for clinical and economic appraisal.

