10.0 Efficacy Analysis

10.1 General Considerations

For all efficacy endpoints, the descriptive statistics including number of observations, mean, standard deviation, minimum, median, and maximum for continuous variables; and number and percent for discrete variables, will be summarized for ITT analysis set. No statistical tests will be performed.

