- Proportion of subjects with SES-CD ≤ 3 and at least 2 point reduction versus Study M14-115 Baseline and no subscore greater than 1 in any individual variable at Week 40 among subjects with SES-CD ≤ 3 and at least 2 point reduction versus Study M14-115 Baseline and no subscore greater than 1 in any individual variable at Week 0 of Study M14-347.
- Proportion of subjects with SES-CD ≤ 3 and at least 2 point reduction versus Study M14-115 Baseline and no subscore greater than 1 in any individual variable at Week 40
- Proportion of subjects with SES-CD = 0 at Week 40 among subjects with SES-CD = 0 at Week 0 of Study M14-347.
- Proportion of subjects with SES-CD = 0 at Week 40.
- Proportion of subjects with a decrease of SES-CD ≥ 3 points from Study M14-115 Baseline at Week 40 among subjects with a decrease of SES-CD ≥ 3 points from Study M14-115 Baseline at Week 0 of Study M14-347.
- Proportion of subjects with a decrease of SES-CD ≥ 3 points from Study M14-115 Baseline at Week 40.
- Proportion of subjects with a decrease in SES-CD $> 50\%$ from Study M14-115 Baseline (or for subjects with an SES-CD of 4 at Study M14-115 Baseline, at least a 2-point reduction from Study M14-115 Baseline) at Week 40 among

subjects with a decrease in SES-CD > 50% from Study M14-115 Baseline (or for subjects with an SES-CD of 4 at Study M14-115 Baseline, at least a 2-point reduction from Study M14-115 Baseline) at Week 0 of Study M14-347.

- Proportion of subjects with a decrease in SES-CD > 50% from Study M14-115 Baseline (or for subjects with an SES-CD of 4 at Study M14-115 Baseline, at least a 2-point reduction from Study M14-115 Baseline) at Week 40.
- Change from Study M14-115 Baseline in hs-CRP level over time.
- Proportion of subjects with Inflammatory Bowel Disease Questionnaire (IBDQ) response (decrease \geq 16 points from Study M14-115 Baseline) over time among subjects with Inflammatory Bowel Disease Questionnaire (IBDQ) response (decrease \geq 16 points from Study M14-115 Baseline) at Week 0 of Study M14-347.
- Proportion of subjects with Inflammatory Bowel Disease Questionnaire (IBDQ) response (decrease \geq 16 points from Study M14-115 Baseline) over time.
- Proportion of subjects with IBDQ remission (IBDQ \geq 170 points) over time among subjects with IBDQ remission (IBDQ \geq 170 points) at Week 0 of Study M14-347.
- Proportion of subjects with IBDQ remission (IBDQ \geq 170 points) over time.
- Change in WPAI from Study M14-115 Baseline over time.

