12.0 Summary of Changes

12.1 Summary of Changes Between the Latest Version of Protocol and the Current SAP

The following efficacy variables are mentioned in the protocol but will not be summarized as they were removed from Study M14-115 protocol:

Proportion of subjects with predicted endoscopic improvement at Week 40, using the 3 definitions and equations.

Correlation between actual SES-CD and Predicted SES-CD:

In addition, change in Bristol Stool Scale score from Baseline over time will not be summarized as Bristol Stool Chart data in ePRO was not collected in Study M14-347.

The following efficacy variables are not mentioned in the protocol but are added to the SAP:

Proportion of subjects with CD related hospitalization: CD related hospitalization is a component of major CD related event.

Proportion of subjects with CD related surgery: CD related surgery is a component of major CD related event.

The following efficacy endpoints are added because they are used in new CD studies.

Proportion of subjects who achieve symptomatic remission, defined as average daily stool frequency ≤ 2.8 (and not worse than Study M14-115 Baseline) and average daily abdominal pain ≤ 1.0 (and not worse than Study M14-115 Baseline) over time among subjects with Study M14-115 Baseline average daily stool frequency ≥ 4.0 or average daily abdominal pain ≥ 2.0 : This endpoint is used for new CD studies as a primary efficacy endpoint.

Proportion of subjects with a decrease in SES-CD $> 50\%$ from Study M14-115 Baseline (or for subjects with an SES-CD of 4 at Study M14-115 Baseline, at least a 2-point reduction from Study M14-115 Baseline) at Week 40.

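### IBDQ response is defined in opposite directions: a fall of at least 16 points in SAP 10.3 but a rise of at least 16 in SAP 6.0, with no rule on which governs

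*SAP*

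**What the plan says.** The direction of IBDQ response is stated in five places in current text.

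**Decrease of at least 16 points**
- Protocol 1.2 (synopsis, additional efficacy endpoints): one bullet.
- Protocol 5.3.3.2: one bullet, worded the same way.
- SAP 10.3: two bullets containing the word three times. Both begin "Proportion of subjects with Inflammatory Bowel Disease Questionnaire (IBDQ) response (decrease". The first continues over time "among subjects with Inflammatory Bowel Disease Questionnaire (IBDQ) response (decrease" of the same size at Week 0, so the definition sets its numerator and its denominator.

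**Increase of at least 16 points**
- Protocol 5.3.3, definitions table: "Increase in IBDQ score", with the same 16-point threshold.
- SAP 6.0, under its heading for the definition of IBDQ response: "Increase in IBDQ \geq 16 from Study M14-115 Baseline".

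Both documents set IBDQ remission at a score of 170 or more. SAP 3.0 says that the SAP "describes analysis conventions to guide the statistical programming work". Protocol 8.1 leaves the detail of the analysis to the SAP.

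**The concern.** The endpoint has two prespecified definitions with opposite signs. SAP 10.3 is the list from which the efficacy tables are built, and its bullets restate the definition in full instead of pointing to SAP 6.0. A programmer working down that list meets decrease used correctly for CDAI and SES-CD in neighbouring bullets, so the word does not stand out in the IBDQ ones.

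Read literally, the all-subjects endpoint would report the share of subjects whose quality of life had worsened by 16 points or more and call it response. The endpoint restricted to Week 0 responders would report persistence of worsening among subjects who had already worsened, under the name of maintained response.

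**Working it through.** The plan gives no figure to reproduce: SAP 4.3 says no sample size was calculated, and neither document gives an IBDQ mean or SD. The check is mainly a comparison of texts.

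**1. Could a different baseline explain the opposite sign?** No. The footnote to the protocol 5.3.3 table, the opening line of protocol 5.3.3.2, SAP 6.0 and SAP 10.3 all use Study M14-115 Baseline.

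**2. Can both definitions hold?** No. With D = visit score minus Baseline score, one requires D ≥ +16 and the other D ≤ −16. No subject satisfies both at one visit.

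**3. Which direction is improvement?** Remission is a score of 170 or more, so higher is better. Under the decrease wording, a responder who is also in remission needs a Baseline score of at least 170 + 16 = 186, already above the remission cut-off. Only the increase wording describes a response.

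**4. Is there a rule of precedence?** No. Protocol 8.1 defers to the SAP, but the SAP contains both directions. The sentence in SAP 3.0 about conventions favours SAP 6.0 without ranking it above SAP 10.3. SAP 12.1, which lists variables dropped from or added to the protocol's set (for example "The following efficacy variables are mentioned in the protocol but will not be summarized"), does not mention IBDQ.

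**5. How many outputs are involved?** SAP Table 4 gives three post-baseline IBDQ visits (Weeks 16, 32 and 40). SAP 10.3 plans NRI with LOCF as sensitivity analysis, and 95% confidence intervals for the proportions. That makes 2 endpoints × 3 visits × 2 methods = 12 post-baseline proportions.

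**6. How far apart are the two readings?** This is an illustration only. Assume D is normal with mean m and SD s, ignoring missing data and censoring. Then

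- increase: P(D ≥ 16) = 1 − Φ((16 − m)/s)
- decrease: P(D ≤ −16) = Φ((−16 − m)/s)

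For m = 20 and s = 30: 1 − Φ(−0.133) = 55.3%, and Φ(−1.2) = 11.5%.

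| Assumed mean | Assumed SD | Increase ≥ 16 | Decrease ≥ 16 |
|---|---|---|---|
| 20 | 30 | 55.3% | 11.5% |
| 20 | 35 | 54.5% | 15.2% |
| 30 | 30 | 68.0% | 6.3% |
| 30 | 35 | 65.5% | 9.4% |
| 40 | 30 | 78.8% | 3.1% |
| 40 | 35 | 75.4% | 5.5% |

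A wider assumed grid (mean 10 to 40, SD 25 to 45) gives 40.5% to 83.1% against 1.3% to 28.2%. With the 252 enrolled subjects stated in SAP 4.2, that is 102 to 210 responders against 3 to 71. If the same distribution held at Week 0, those counts would also be the two candidate denominators for the maintained-response endpoint.

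Missing data, dose escalation and the corticosteroid rule would lower both columns under NRI, since "all missing values will be considered as 'Not Achieved" and SAP 6.0 treats censored subjects as non-responders whichever sign is used. The size of that reduction depends on how these events relate to IBDQ change. Escalation requires CDAI of 200 or more, so independence is doubtful, and no adjusted figures are given here.

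**The case against.** The strongest reply is that the intended meaning is hardly in doubt. The two places whose job is to define terms, the protocol 5.3.3 table and the headed definition in SAP 6.0, agree on increase. Decrease appears only in parentheses in endpoint lists, and SAP 10.3 looks like protocol wording carried over. With remission at 170 or more, only one reading makes clinical sense. This stands as the likely explanation and tells us which wording is wrong. It does not remove the conflict, because SAP 10.3 gives a complete definition of its own and nothing says that SAP 6.0 overrides it.

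A second reply is that SAP 12.1 has nothing to report, since on direction the SAP only reproduces the protocol's own inconsistency. That is fair. The silence of SAP 12.1 is not a separate defect, and an entry is needed only once the wording is corrected.

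A third is that little depends on it. These are additional descriptive endpoints, SAP 10.1 states "No statistical tests will be performed", and a reversed table would clash visibly with IBDQ remission and mean change in IBDQ. This also stands and limits the weight of the point. It does not justify leaving an endpoint specified in the wrong direction.

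Finally, the percentages rest on assumptions and do not bound the effect. They show only that the two readings would give very different tables.

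**Conclusion.** The contradiction is real and lies in current text of both documents. The decrease wording is wrong on the documents' own evidence, because remission is defined by a high score. Followed literally, SAP 10.3 would count worsening as response in both IBDQ-response endpoints and would build the maintained-response denominator from worsened subjects. If SAP 6.0 is followed, the results are correct.

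The conclusion rests on the text and needs no numerical assumption. Only the illustrated gap depends on the assumed normal distribution, mean and SD. The primary endpoint, IBDQ remission and change in IBDQ do not depend on the sign. This is a correction that should be made, confined to non-primary descriptive results.

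**What to change.** In SAP 10.3, replace decrease with increase at all three IBDQ-response occurrences, including the Week 0 denominator. Alternatively, delete the parentheses and cite the SAP 6.0 definition. SAP 10.3 already does something similar for endoscopic response, which it names without restating the definition.

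Add one entry to SAP 12.1 recording that the synopsis and protocol 5.3.3.2 say decrease, that protocol 5.3.3 says increase, and that increase is used. The sponsor should also confirm which sign the analysis programs apply.

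The cost is three words and one entry, with no change to data collection or method. The protocol wording needs correcting only if the protocol is amended again. The SAP already describes enrolment in the past tense, so the SAP correction is the one that matters.

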5.3.3.2 Additional Efficacy Variables

For additional efficacy endpoints, the baseline is defined as the Baseline in Study M14-115.

- Proportion of subjects with CDAI remission (CDAI $<$ 150) at Week 40 among subjects with CDAI remission at Week 0 of Study M14-347.
- Proportion of subjects with a SFPS remission (SFPS $<$ 50) at Week 40 among subjects with SFPS remission at Week 0 of Study M14-347.
- Proportion of subjects who achieve CDAI remission (CDAI $<$ 150) over time.
- Time in CDAI remission (CDAI $<$ 150) for subjects in CDAI remission at Week 0 of Study M14-347.
- Time to achieve CDAI remission (CDAI $<$ 150) for subjects who were not in CDAI remission at Week 0 of Study M14-347.
- Time to first dose escalation.

- Proportion of subjects who require weekly dosing at Week 1 of Study M14-347.
- Time to achieve SFPS remission (SFPS < 50) for subjects who were not in SFPS remission at Week 0 of Study M14-347.
- Time in SFPS remission (SFPS < 50) among subjects with SFPS remission at Week 0 of Study M14-347.
- Proportion of subjects who achieve a Simplified Endoscopic Score for Crohn's Disease (SES-CD \leq 4) with an Ulcerated Surface subscore no greater than 1 in any segment at Week 40.
- Proportion of subjects who achieve a SFPS < 50 over time.
- Proportion of subjects who entered Study M14-347 who were taking corticosteroids at Week 0 of Study M14-115 who discontinue corticosteroid use and achieved CDAI remission (CDAI < 150) at Week 40.
- Proportion of subjects who entered Study M14-347 who were taking corticosteroids at Week 0 of Study M14-115 who discontinue corticosteroid use at each visit.
- Proportion of subjects with CDAI response (decrease in CDAI \geq 70 points from Baseline) over time.
- Proportion of subjects with enhanced CDAI response (decrease in CDAI \geq 100 points from Baseline) over time.
- Proportion of subjects with endoscopic response (decrease \geq 50% SES-CD from Baseline) at Week 40.
- Proportion of subjects with Inflammatory Bowel Disease Questionnaire (IBDQ) response (decrease \geq 16 points from Baseline) over time.
- Proportion of subjects with IBDQ remission (IBDQ \geq 170 points) over time.
- Change in IBDQ from Baseline over time.
- Change from Baseline in fecal calprotectin level over time.
- Change from Baseline in hs-CRP level over time.
- Proportion of subjects with hs-CRP < 5 mg/L and fecal calprotectin < 250 μ g/g over time.

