- Proportion of subjects with CDAI < 150, hs-CRP < 5 mg/L, and fecal calprotectin < 250 µg/g over time.
- Proportion of subjects with CDAI < 150, hs-CRP < 5 mg/L, SES-CD ≤ 4 with an Ulcerated Surface subscore no greater than 1 in any segment, and fecal calprotectin < 250 µg/g over time.
- Change in WPAI from Baseline over time.
- Change in European Quality of Life 5 Dimensions (EQ-5D) from Baseline over time.
- Change in CDAI from Baseline over time.
- Change in SFPS from Baseline over time.
- Change in Abdominal Pain Rating Scale score from Baseline over time.
- Proportion of subjects with major CD related event (e.g., hospitalization, bowel surgery, abscess drainage).
- Proportion of subjects with SES-CD = 0 at Week 40.
- Proportion of subjects with a decrease of SES-CD ≥ 3 points from Baseline of Study M14-115 at Week 40.
- Change in each CDAI component subscore (number of liquid or very soft stools, abdominal pain rating, general well-being, CD related complications, anti-diarrhea use, abdominal mass, hematocrit, body weight) from Baseline over time.
- Proportion of subjects requiring dose escalation to weekly dosing during this study.
- The proportion of subjects with no draining fistulas over time among subjects with draining fistula at Baseline of Study M14-115.
- The proportion of subjects in each treatment group with ≥ 50% reduction from Baseline of Study M14-115 in the number of draining fistulas over time among subjects with draining fistula at Baseline of Study M14-115.
- Proportion of subjects with CDAI < 150 at Week 40 and SES-CD ≤ 4 with an ulcerated surface subscore no greater than 1 in any segment at Week 40.
- Change in presence of extraintestinal manifestations over time.

- Proportion of subjects with predicted endoscopic improvement at Week 40, using the 3 definitions and equations listed below:

1. Index score predicting the mucosal ulceration status (presence/absence) developed using retrospective CDEIS (≤ 4.24 versus > 4.24), laboratory and patient questionnaire data. The CDEIS based prediction index score is defined as
$$P_{CDEIS} = \exp(A) / [1 + \exp(A)], \text{ where}$$
$$A = 2.0291 - 0.0432 * \text{Age} + 0.0429 * \text{Albumin (g/L)} - 0.0060 * \text{Platelet Count (10}^9/\text{L}) - 0.3286 * \text{CRP (mg/dL)} - 0.0058 * \text{CDAI1} - 0.001 * \text{CDAI3},$$

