10.3 Additional Efficacy Analyses

For additional efficacy endpoints, the baseline is defined as the Baseline in Study M14-115. The additional efficacy variables are listed as below.

- Proportion of subjects with CDAI remission (CDAI < 150) over time among subjects with CDAI remission at Week 0 of Study M14-347.
- Proportion of subjects with endoscopic improvement, defined as an SES-CD ≤ 4 and at least 2 point reduction versus Study M14-115 Baseline and no subscore greater than 1 in any individual variable at Week 40.
- Proportion of subjects with CDAI remission (CDAI < 150) over time.
- Proportion of subjects with CDAI < 150 at Week 40 and SES-CD ≤ 4 and at least a 2 point reduction versus Study M14-115 Baseline and no subscore greater than 1 in any individual variable at Week 40 among subjects with CDAI < 150 at Week 0 and SES-CD ≤ 4 and at least a 2 point reduction versus Study M14-115 Baseline and no subscore greater than 1 in any individual variable at Week 0 of Study M14-347.
- Proportion of subjects with CDAI < 150 at Week 40 and SES-CD ≤ 4 and at least a 2 point reduction versus Study M14-115 Baseline and no subscore greater than 1 in any individual variable at Week 40.
- Proportion of subjects with endoscopic response at Week 40 among subjects with endoscopic response at Week 0 of Study M14-347.
- Proportion of subjects with endoscopic response at Week 40.
- Change from Study M14-115 Baseline in fecal calprotectin level over time.

- Proportion of subjects with hs-CRP < 5 mg/L and fecal calprotectin < 250 µg/g over time among subjects with hs-CRP < 5 mg/L and fecal calprotectin < 250 µg/g at Week 0 of Study M14-347.
- Proportion of subjects with hs-CRP < 5 mg/L and fecal calprotectin < 250 µg/g over time.
- Proportion of subjects with CDAI < 150, hs-CRP < 5 mg/L, and fecal calprotectin < 250 µg/g over time among subjects with CDAI < 150, hs-CRP < 5 mg/L, and fecal calprotectin < 250 µg/g at Week 0 of Study M14-347.
- Proportion of subjects with CDAI < 150, hs-CRP < 5 mg/L, and fecal calprotectin < 250 µg/g over time.

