- Change in European Quality of Life 5 Dimensions (EQ-5D) from Study M14-115 Baseline over time.
- Change in CDAI from Study M14-115 Baseline over time.
- Change in SFPS from Study M14-115 Baseline over time.
- Change in Abdominal Pain Rating Scale score from Study M14-115 Baseline over time.
- Change in each CDAI component subscore (number of liquid or very soft stools, abdominal pain rating, general well-being, CD related complications, anti-diarrhea use, abdominal mass, hematocrit, body weight) from Study M14-115 Baseline over time.
- Time to first dose escalation.

- Proportion of subjects who require weekly dosing at Week 1 of Study M14-347.
- Proportion of subjects with major CD related event (e.g., hospitalization, bowel surgery, abscess drainage).
- Proportion of subjects with CD related hospitalization.
- Proportion of subjects with CD related surgery.
- Proportion of subjects requiring dose escalation to weekly dosing during this study.
- Proportion of subjects with no draining fistulas over time among subjects with draining fistula at Study M14-115 Baseline.
- Proportion of subjects in each treatment group with > 50% reduction from Baseline of Study M14-115 in the number of draining fistulas over time among subjects with draining fistula at Study M14-115 Baseline.
- Resolution of extraintestinal manifestations over time.
- Proportion of subjects who achieve symptomatic remission, defined as average daily stool frequency ≤ 1.5 (and not worse than Study M14-115 Baseline) and average daily abdominal pain ≤ 1.0 (and not worse than Study M14-115 Baseline) over time among subjects with Study M14-115 Baseline average daily stool frequency ≥ 2.5 or average daily abdominal pain ≥ 2.0 .
- Proportion of subjects who achieve symptomatic remission, defined as average daily stool frequency ≤ 2.8 (and not worse than Study M14-115 Baseline) and average daily abdominal pain ≤ 1.0 (and not worse than Study M14-115 Baseline) over time among subjects with Study M14-115 Baseline average daily stool frequency ≥ 4.0 or average daily abdominal pain ≥ 2.0 .
- Proportion of subjects who achieve symptomatic response, defined as average daily stool frequency at least 30% reduction from Study M14-115 Baseline and average daily abdominal pain not worse than Study M14-115 Baseline or average daily abdominal pain at least 30% reduction from Study M14-115 Baseline and average daily stool frequency not worse than Study M14-115 Baseline, over time.

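### The SAP moves endoscopic response and draining-fistula reduction from at least 50% to more than 50% without declaring it, which reclassifies every subject who improves by exactly half

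*SAP*

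**What the plan says.** **Endoscopic response.** The definition table in Protocol 5.3.3 gives "Decrease \geq 50% SES-CD from Baseline". The synopsis and the endpoint list in Protocol 5.3.3.2 repeat the same threshold ("decrease \geq 50% SES-CD from Baseline"). SAP 6.0 defines endoscopic response as "Decrease in SES-CD $>$ 50% from Study M14-115 Baseline". SAP 10.3 then uses the term by name, without restating the threshold, in two endpoints: one for all subjects ("Proportion of subjects with endoscopic response at Week 40") and one restricted to subjects who were already responders at Week 0.

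**Draining fistulas.** The synopsis and Protocol 5.3.3.2 ask for the proportion "with ≥ 50% reduction from Baseline of Study M14-115 in the number of draining fistulas over time". SAP 10.3 has "Proportion of subjects in each treatment group with > 50% reduction from Baseline of Study M14-115 in the number of draining fistulas over time". Directly before it, SAP 10.3 lists the full-closure endpoint: "Proportion of subjects with no draining fistulas over time among subjects with draining fistula at Study M14-115 Baseline".

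**Declared changes.** SAP 12.1 sets out differences from the latest protocol. It does not mention the fistula threshold or a new definition of endoscopic response. It does list an SES-CD endpoint at more than 50%, with an allowance of a 2-point fall for subjects whose baseline score is 4, and presents it as an addition taken from newer Crohn's disease studies.

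**The concern.** Two endpoints keep their protocol names but are scored by a stricter rule, and the section meant to disclose such changes is silent. A reader of 12.1 would conclude that endoscopic response is still the protocol's endpoint and that the version at more than 50% is an extra.

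SES-CD totals and fistula counts are whole numbers, so an exact halving is an ordinary outcome rather than a rounding curiosity. At stake is whether the reported proportions, each with a 95% confidence interval under SAP 10.3, are the ones the protocol promised. For subjects with 2 fistulas at baseline, there is also the question of whether the reduction endpoint says anything beyond the closure endpoint listed beside it.

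**Working it through.** The plan gives no figure to reproduce: SAP 4.3 reports that no sample size was calculated, and SAP 10.1 that no tests are done. The check is an enumeration of whole-number outcomes, followed by illustrations under assumptions.

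**Rule.** For baseline value b and later value r, the protocol counts success if 2(b − r) ≥ b and the SAP if 2(b − r) > b. They differ only when 2r = b, which needs an even b.

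**Fistulas: remaining counts that qualify**

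| Baseline | Protocol | SAP | Is the SAP rule full closure? |
|---|---|---|---|
| 1 | 0 | 0 | Yes, and already so under the protocol |
| 2 | 0, 1 | 0 | Yes, newly so |
| 3 | 0, 1 | 0, 1 | No |
| 4 | 0, 1, 2 | 0, 1 | No |
| 5 | 0, 1, 2 | 0, 1, 2 | No |
| 6 | 0, 1, 2, 3 | 0, 1, 2 | No |

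Illustration for a subject with exactly 2 fistulas, assuming each closes independently with probability 0.5: protocol response is 1 − 0.5² = 75%; SAP response is 0.5² = 25%. The distribution of baseline counts is not in the documents, so this is not a forecast for the endpoint as a whole.

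**SES-CD: highest later score that qualifies**

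| Baseline | Protocol | SAP endoscopic response | SAP added variant (baseline-4 allowance) |
|---|---|---|---|
| 4 | 2 | 1 | 2 |
| 6 | 3 | 2 | 2 |
| 8 | 4 | 3 | 3 |
| 10 | 5 | 4 | 4 |

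Odd baselines give the same cut-off under all three. The added variant recovers the protocol's classification at a baseline of 4 only, so no endpoint in SAP 10.3 applies the protocol's definition across all baselines.

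**Direction.** In the whole cohort the denominator is fixed and the strict rule can only remove responders, so the proportion falls or is unchanged. Among Week 0 responders the strict rule also removes from the denominator anyone at exactly 50% at Week 0. Let x of n such subjects respond at Week 40. Dropping one who fails at Week 40 changes x/n to x/(n − 1), which is higher when x > 0. Reclassifying one who is at exactly 50% at Week 40 changes it to (x − 1)/n, which is lower.

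**Size by number affected.** With k subjects at exactly 50% on SES-CD among the 252 enrolled (SAP 4.2), the whole-cohort proportion falls by k/252: 0.4 points for k = 1, 2.0 for k = 5, 4.0 for k = 10 and 9.9 for k = 25. The values of k are assumed.

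**Size by simulation.** Assumptions: baseline SES-CD uniform on the integers 6 to 24; Week 40 score = baseline × median ratio × lognormal error, rounded to an integer; median ratio 0.4, 0.5 or 0.6; 1,000,000 draws per setting.

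| Log-SD | Gap over ratios 0.4 to 0.6 (points) | Example at ratio 0.5, protocol vs SAP |
|---|---|---|
| 0.3 | 8.6 to 11.0 | 55.2% vs 44.2% |
| 0.5 | 6.1 to 6.7 | 53.2% vs 46.5% |
| 0.7 | 4.6 to 4.8 | 52.2% vs 47.4% |
| 1.0 | 3.3 to 3.4 | 51.5% vs 48.2% |

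The overall range is about 3 to 11 points, driven mainly by the assumed spread. Subjects with missing data, dose escalation or censoring for steroid use are non-responders under either rule. If a share q of subjects falls there, the gap is multiplied by (1 − q). At an assumed q = 0.5 it becomes about 1.7 to 5.5 points (3.3 × 0.5 and 11.0 × 0.5).

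**The case against.** Four points can fairly be made for the plan.

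- **The consequence is limited.** Both are additional, descriptive endpoints in a single-arm open-label extension. The primary endpoint uses neither threshold, and no test or decision rule depends on them. This stands, and it limits the weight of the point without removing it.
- **The stricter SES-CD criterion is visible in 12.1.** It is, but as an added endpoint. That does not tell the reader that the existing endoscopic response endpoint was redefined as well.
- **The two operators may have different origins.** The SES-CD sign looks intended: a fall from 4 to 2 is exactly 50%, so the baseline-4 allowance would be unnecessary under at least 50%. The fistula sign has no such support and may be a typing slip. This also stands, but a programmer would code what is written, so the text needs correcting in either case.
- **The sizes are illustrative.** They are. Neither the number of subjects at exactly 50% nor the distribution of fistula counts is given.

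A reader might also infer that the change makes fistula reduction the same as closure for anyone with 1 or 2 fistulas, and so empties the endpoint of meaning. The documents do not support that. With 1 fistula, at least 50% already means closure under the protocol. With 3 or more, reduction and closure still differ under the SAP, since going from 3 to 1 qualifies as reduction.

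**Conclusion.** The discrepancy is real. Both thresholds move from at least 50% to more than 50%, 12.1 declares neither, and every subject at exactly 50% is classified differently from the protocol. The arithmetic establishes the direction for whole-cohort proportions: down or unchanged. It would be natural to say that the SAP lowers both endpoints, but that goes too far. A fall requires at least one subject at exactly 50%, a number the documents do not give, and the proportion among Week 0 responders can move either way.

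The SES-CD gap of about 3 to 11 points rests on the assumed baseline range, median ratio and spread, and applies before imputation and censoring. The 75% versus 25% contrast applies only to subjects with exactly 2 fistulas under the assumed closure chance. The primary result is not affected. The point is worth correcting because protocol-defined endpoints would otherwise be reported under their own names with a different rule.

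**What to change.** In SAP 6.0, set endoscopic response at a decrease of at least 50% from the Study M14-115 baseline, so that both endpoints in 10.3 that use the term follow it. In SAP 10.3, set the fistula reduction endpoint at at least 50%. If the sponsor wants the SES-CD criterion of more than 50%, keep it, including the variant with the baseline-4 allowance, under a separate name, and state in 12.1 that it is additional to the protocol's endoscopic response.

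The cost is SAP wording, one comparison operator in the code, and at most one extra table row per endpoint. No new data are needed.
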